Clients will be assigned to home visitors according to usual site procedures. Home visitors will introduce the study to all clients who meet eligibility criteria (English or Spanish speaking; 18 or older; pregnant or within 3 months postpartum; enrolled in HFA within the prior 6 months) at the enrollment visit (for newly enrolling clients) or at the next available visit (for clients already enrolled within the prior six months) using a script provided by study staff. Home visitors will ask clients for their permission to provide their contact information to the study team. If permission is granted, the home visitor will provide the client's contact information to a study RA, who will contact the client by phone and conduct a brief eligibility screen (data will be retained anonymously). Home visitors will also give clients the option to contact the study team themselves, if they prefer, rather than having home visitors provide their contact information to the study team. If the client is eligible, the study RA will explain the study in more detail and ask the client if she is interested in enrolling. If the client says yes, the RA will send the client a link to a pdf copy of the informed consent form via email or text (depending on client preference). After giving the client a few minutes to review the consent form, the RA will review the main points in the consent form and ask the client if she has any questions. After answering all questions, the RA will ask the client if she would like to decide now whether or not to enroll, or would like to take more time and receive a call back later from the RA. If the client would like more time, the RA will call the client back at a time specified by the client. Once the client decides to enroll, the RA will ask her to sign the pdf of the consent form using DocuSign and send it back to the RA. The RA will then sign as a witness, and send the pdf to the PI for her signature, also using DocuSign. After obtaining all signatures, the RA will send a final signed pdf of the consent form back to the client for her records. After the informed consent process is complete, the RA will either send the client a link to complete the baseline assessment online (via a Qualtrics survey), or schedule an appointment to complete the baseline assessment with the client via phone or video-conference, depending on the client's preference. Signing informed consent and completing the baseline assessment constitutes enrollment into the study. Clients are assigned to whichever study condition their home visitor is assigned to.

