Timeframe	Activity	Person Responsible
Home Visitor Recruitment, Enrollment, and Training [October 2020-December 2020]		
At Quarterly Supervisors' Meeting in October	HELP staff introduce study to HFA supervisors at Quarterly Supervisors' Meeting (via Zoom)	PI, RAs
Scheduled for Oct-Nov 2020	HELP staff introduce study to home visitors in NJ HFA network (via Zoom)	PI, RAs
	Home visitors sign informed consent and enroll in study via individual Zoom meetings with PI	PI, RAs
	Home visitors are randomized to condition	PI
After home visitors enroll [Dec 2020]	Home visitor training [pre-recorded videos plus live zoom sessions]-intervention and control groups trained separately	PI, RAs, Home visitors
Client Recruitment and Enrollment [January 2021-October 2021]		
At HFA enrollment visit OR next visit after client is identified as eligible	Home visitors introduce study (using script) to all clients meeting eligibility criteria: newly enrolling or enrolled within the last 6 months; speak English or Spanish; 18 years or older; pregnant or within 3 months postpartum.	Home visitors
Weekly	Home visitors provide client contact information to HELP staff	Home visitors
Ongoing	HELP RAs contact client, conduct eligibility screen, and obtain informed consent from eligible clients who are interested in participating.	RAs
Within 1 week of consent	Client completes baseline assessment [either via Qualtrics link or via phone with RA, depending on client preference]	RAs, Clients
Upon completion of baseline	RA informs home visitor that client has enrolled and completed baseline interview and to do Introduction at next home visit (content differs by condition)	RAs
Implementation of HV-SBI Components [January 2021-December 2021]		
At next home visit	Home visitor completes Introduction: Alcohol & Other Drugs (for intervention group) OR Introduction: Nutrition (for control group)	Home visitor
After home visit	RA sends home visitor text-based fidelity checklist to determine whether Introduction was completed	RAs

	Home visitor completes text-based fidelity checklist	Home visitor
Within 2 weeks of baseline	RA prompts client to complete HELP Session 1 (content differs by condition) within 2 weeks of baseline date and provides technical support by phone or text as needed	RAs
Within 2 weeks of baseline	Client completes HELP Session 1	Clients

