Upon completion of HELP Session 1	RA informs home visitor that client has completed HELP Session 1 and to do HELP Debrief 1 AND Introduction to session 2 at next home visit (content differs by condition)	RAs
At next home visit	Home visitor completes Debrief: Alcohol & Drugs (for intervention group) OR Debrief: Nutrition (for control group) AND Introduction: Other Concerns (for intervention group) OR Introduction: Exercise (for control group)	Home visitors
After home visit	RA sends home visitor text-based fidelity checklist to determine whether HELP Debrief 1 was completed	RAs
	Home visitor completes text-based fidelity checklist	Home visitors
Within 2 weeks of HELP Session 1	RA prompts client to complete HELP Session 2 (content differs by condition) within 2 weeks after completing HELP Session 1 and provides tech support by phone or text as needed	RAs
Within 2 weeks of HELP Session 1	Client completes HELP Session 2	Clients
Upon completion of HELP Session 2	RA informs home visitor that client has completed HELP Session 2 and to do HELP Debrief 2 at next home visit (content differs by condition)	RAs
At next home visit	Home visitor completes Debrief: Other Concerns (for intervention group) OR Debrief: Exercise (for control group)	Home visitors
After home visit	RA sends home visitor text-based fidelity checklist to determine whether HELP Debrief 2 was completed	RAs
	Home visitor completes text-based fidelity checklist	Home visitors
Follow-Up Interviews [April 2021-March 2022]		
After completion of entire HELP intervention	RA conducts qualitative interviews with home visitors and clients (random sample from intervention condition only) on zoom.	RAs, Clients, Home visitors
3 months after baseline	Client completes 3-month follow-up assessment (either via online survey or phone, depending on client preference)	RAs, Clients
6 months after baseline	Client completes 6-month follow-up assessment (either via online survey or phone, depending on client preference)	RAs, Clients

DATA COLLECTION AND TRACKING PROCEDURES

Data Tracking

We will use Partnership to End Addiction's JITAI Master Platform for tracking participants through the study. This platform has previously been used in NIH and foundation research studies

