item measure of stress associated with parenting that is widely used in longitudinal studies of parenting and HV. Secondary study outcomes (assessed at baseline, 3-mo, and 6-mo follow-up) include home visiting retention, home visitor-client relationship, substance use treatment engagement, child protective services reports, and conversations about substance use during home visits. HV retention, CPS reports, and conversations about SU will be mined from the HFA MIS. SU Treatment Engagement will be assessed at 6-month follow-up via the *Treatment Services Review*. Additional variables that are potential moderators of impact include: motivation to change, intimate partner violence, social support, and stress. Motivation to change substance use will be measured with the Maternal Motivation Scale. Intimate partner violence will be measured with the Composite Abuse Scale. Social support will be measured with the Interpersonal Support Evaluation List (ISEL-12), and stress will be measured with the Perceived Stress Scale. All are validated measures that have been widely used in other studies of pregnant and postpartum women. The strength of the relationship between home visitors and clients will be measured via the Working Alliance Inventory-Short Form, Client Version (WAI-SC). The WAI-SC is a 12-item measure of client perceptions of trust in their provider and of agreement on goals and tasks, and has demonstrated good psychometric properties in the HV context.

DATA ANALYSIS

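### Does a follow-up heading that ends in March 2022 cut off the 6-month assessment of clients enrolled in October 2021?

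*Combined protocol and SAP*

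**What the plan says.** The table under Timeline of Study Activities is divided into blocks, each headed by a range of months. One block is headed "Client Recruitment and Enrollment [January 2021-October 2021" and a later one "Follow-Up Interviews [April 2021-March 2022". The baseline assessment has its own row in the enrolment block, timed "Within 1 week of consent". The 3-month and 6-month assessments are rows in the follow-up block, and each is timed from the client's own baseline. The last of them is the row "Client completes 6-month follow-up assessment", set at 6 months after baseline.

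The Clients part of Recruitment, Enrollment and Randomization Procedures defines enrolment: "Signing informed consent and completing the baseline assessment constitutes enrollment into the study". Study Purpose and Aims and Outcome Data Collection repeat the baseline, 3-month and 6-month schedule for all clients without a calendar limit.

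**The concern.** If enrolment can run to the end of October 2021 and includes the baseline, the last 6-month assessments fall in April 2022, one month after the follow-up heading ends. The table then seems to give two answers for October enrolees. The per-client row says to assess them in April; the heading, read as a limit, says follow-up is over by then.

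If the heading won, those clients would miss the 6-month assessment or have it early. Under the preferred growth model with full information maximum likelihood, they would still contribute baseline and 3-month data. Under the fallback in Data Analysis, a separate ANOVA at each follow-up, a client without a 6-month value would drop out of the 6-month comparison. In a trial planned for 40 clients, losing a few in that way would be worth preventing.

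**Working it through.** **Inputs**
- Enrolment window: January to October 2021, 10 calendar months (timeline table).
- Enrolment requires consent and a completed baseline (Recruitment, Enrollment and Randomization Procedures).
- Assessments at baseline + 3 months and baseline + 6 months (timeline table).
- Stated follow-up window: April 2021 to March 2022, 12 calendar months (timeline table).
- Planned clients: 40 (Study Purpose and Aims).

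**Start of the window**

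First enrolment month + 3 months = January 2021 + 3 = April 2021. This reproduces the heading.

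**End of the window**

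Last enrolment month + 6 months = October 2021 + 6 = April 2022. The heading says March 2022, so this does not reproduce.

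| Baseline | 3-month assessment | 6-month assessment | Days after 31 March 2022 |
|---|---|---|---|
| 30 September 2021 | 30 December 2021 | 30 March 2022 | −1 (inside) |
| 1 October 2021 | 1 January 2022 | 1 April 2022 | 1 |
| 31 October 2021 | 31 January 2022 | 30 April 2022 | 30 |

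Months needed = 10 + (6 − 3) = 13, against 12 stated. The heading is one calendar month short, at the end only. October enrolees' 3-month assessments fall inside it.

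Counting enrolment from consent alone would not close the gap. Consent on 31 October with a baseline one week later, on 7 November, puts the 6-month assessment on 7 May 2022, 37 days past 31 March.

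**Which heading slipped**

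The implementation block ends in December 2021. A 31 October baseline plus two 2-week session periods reaches 28 November 2021, which fits. That is compatible with enrolment through October, but it does not prove that the follow-up heading is the one in error.

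**How many clients**

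The document gives no accrual curve. Assuming even accrual from 1 January to 31 October 2021:
- October share = 31 / 304 days = 10.2%.
- Clients = 0.102 × 40 ≈ 4.1.

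If October held 5% to 20% of accrual (an assumed range), the count is 0.05 × 40 = 2 to 0.20 × 40 = 8. October is an outer limit for recruitment; had the target been met by the end of September, the count would be 0.

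**What happens to them**
- Per-client rule followed: assessed in April 2022 at 6 months, with no data lost.
- Heading treated as a hard stop: assessed 1 to 30 days early, or not at all. For a 31 October baseline, an assessment on 31 March 2022 comes at 151 days, not 181.

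The second outcome needs a rule that the document does not contain. No last-visit date, data lock or shortened follow-up for late enrolees is given. Data Tracking says that assessment links go out when each client is due, which is also a per-client trigger.

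**The case for a change.** The strongest case for a change is that the arithmetic leaves no escape. Even the most favourable October date, the 1st, misses the heading, and no visit window is stated that would absorb the difference. The labels are whole months and the gap is a whole month, so loose rounding does not explain it. The correction would cost one line. All of that stands as a description of the table.

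The claimed harm does not stand. It requires staff to set aside an explicit instruction timed from each client's baseline in favour of a month label above it, and nothing tells them to do so. The loss under the ANOVA fallback depends on the same step.

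Nor does it help to single out substance use treatment engagement as the outcome most at risk. Client Measures does say "SU Treatment Engagement will be assessed at 6-month follow-up via the" Treatment Services Review. It also lists that outcome among the secondary outcomes assessed at baseline, 3 months and 6 months. The section therefore makes two statements on its timing, and a claim that it is measured only at 6 months uses just one of them.

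**Conclusion.** The two headings disagree by one month, and that much is certain from the dates. It is a clerical slip in a planning table and calls for no change to the plan. The operative rule is 6 months after each client's baseline; followed as written, it carries October enrolees into April 2022 and loses no data. Correcting the label would alter no sample size, endpoint or analysis, and no source of bias or safety matter.

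The number of clients who could be touched runs from 0 to a few of 40: about 4 under assumed even accrual, and up to 8 if October held 20% of accrual. Even these would be affected only if the heading were enforced as a cut-off, which the document does not require. In the event, the opening note reports 14 enrolled participants, randomisation eliminated and the planned longitudinal analyses not carried out, so the projected loss concerns a sample that was never recruited.

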The primary study aim is to conduct a pilot randomized controlled trial (RCT) to (1) assess feasibility, acceptability, and fidelity of SBI-HV, and (2) determine the preliminary impacts of SBI-HV on client symptom reduction (SU, depression, parenting stress), retention in HV, engagement in SU treatment, and alliance between the home visitor and client. The pilot RCT will be conducted in New Jersey, in counties that are implementing the Healthy Families America (HFA) home visiting program. We will enroll 20 home visitors and 40 clients. The pilot RCT will be a cluster-randomized trial, with home visitors randomly assigned to study condition. Feasibility, acceptability, and fidelity will be assessed via home visitor and client interviews and fidelity checklists. Clients will be assessed at baseline, and 3- and 6-month follow-up to track SBI-HV impacts on outcomes.

STUDY PARTICIPANTS

The study will be conducted within New Jersey (NJ)'s HV system within the Healthy Families America (HFA) HV program. Participation will be offered to all HFA home visitors throughout the state

Home Visitors

We will enroll 20 HFA home visitors in the trial. Based on our prior research with this population, we expect the home visitors to have the following demographic characteristics: 100% female, average age 36 years, 25% White, 40% Latina, 30% Black, average 5 years HV experience, and 60% with greater than a high school education.

Clients

We will enroll 40 clients who meet the following study eligibility criteria: (1) speak English or Spanish; (2) age 18 years old or older; (3) pregnant or up to 3 months postpartum; (4) enrolled in HFA with a participating home visitor within the prior six months; (5) reporting binge drinking or illicit drug use in the 3 months prior to their most recent pregnancy and not currently attending substance use treatment; and (6) have access to smartphone or other internet-enabled device with internet connection. Based on prior work with this population, we expect clients to have the following demographic characteristics: 40% Latina, 41% White, 34% Black,

63% single, 22% with a high school education or less, 78% unemployed, 85% on public assistance, and 15% child welfare system-involved.

STUDY CONDITIONS AND HV-SBI COMPONENTS FOR EACH CONDITION

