Home visitors will be randomly assigned to Intervention or Control conditions, and clients will be assigned to whichever condition their home visitor is in. SBI-HV components that will be added on to routine HFA services include (1) electronic screening and brief intervention (e-SBI); (2) Home Visitor Facilitation; and (3) Technical Support. Table 1 details which study component clients in each condition will receive. The primary difference between conditions will be in the content of the e-SBI and home visitor facilitation components. A detailed description of each SBI-HV component follows the table.

Table 1. SBI-HV Components by Study Condition

Intervention Condition	Control Condition
Routine HFA Services	Routine HFA Services
e-SBI Session 1: Substance Use e-SBI Session 2: Co-occurring Problems	e-SBI Session 1: Nutrition e-SBI Session 2: Exercise
Home Visitor Facilitation: Introduction and de-brief before and after each e-SBI session (content related to substance use and co-occurring problems)	Home Visitor Facilitation: Introduction and de-brief before and after each e-SBI session (content related to nutrition and exercise)
Technical support provided by research staff	Technical support provided by research staff

Routine HFA Services

HFA is an evidence-based, voluntary, HV program designed to promote positive parenting, enhance child health and development, and prevent child maltreatment in at-risk families that serves families prenatally up to age 5 years. Home visits (approximately 1 hour each) occur weekly for the first 6 months, tapering in frequency over time depending on the family's level of functioning, and follow a structured curriculum. Model implementation follows the HFA Best Practice Standards, operationalized through structured program guidelines that are flexibly tailored to families' needs. HFA mandates a quality assurance and accreditation process for program sites, thus an infrastructure for fidelity monitoring and CQI is already in place. Federally-funded HFA sites are also required to track and report progress on federally-specified benchmarks. All of the NJ HFA sites are accredited and federally-funded and have extensive data tracking and CQI procedures in place. Home visitors and supervisors routinely complete logs after each visit and supervision session and data is maintained in an electronic Management Information System (MIS) managed by PCANJ.

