The HFA national model requires a minimum of a high school diploma plus relevant experience for home visitors and a Masters degree or BA with 3 years experience for supervisors. Training is required for home visitors (4 days) and supervisors (2 days) at initial hire with annual refreshers. In NJ, all HFA training is provided by PCANJ. As required by the HFA standards, all full-time home visitors receive 2 hours of individual supervision per week. Per the HFA Standards, each supervision session must include administrative (i.e., oversight of program policies; adherence to standards), clinical (i.e., discussing families' challenges; providing guidance and coaching; evaluating progress), and reflective (i.e., attending to home visitors' emotional reactions) components.

Families are eligible for enrollment in HFA if they are prenatal or within 2 weeks of the baby's birth, and if they have two or more risk factors associated with child maltreatment (e.g., inadequate income, unstable housing, history of substance abuse, no prenatal care, history of depression or psychiatric care). Note that these eligibility criteria pertain to enrollment in the HFA program and are different from eligibility criteria to enroll in the research study described in this protocol (detailed on page 3). Supervisors assign clients to home visitors based on the home visitor's experience and skill, difficulty level of the family, and home visitor's current caseload. Home visitor caseload size is 13-26 families, varying based on the service needs of each family.

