SBI-HV Impacts on Client Outcomes. The study will use a randomized intent-to-treat design, with home visitors randomly assigned to condition (routine HV vs. HV+SBI-HV). Data will have a 3-level nested structure: clients (N=40) within home visitors (N=10-20) within sites. Given the small number of home visitors and sites, modeling each as a random effect would not yield stable estimates. Therefore, we will use the sandwich variance estimator to adjust standard errors as appropriate to account for nesting of clients within home visitors. Site will be included as a fixed covariate in all models. We will conduct ANOVA or chi-square tests to assess group equivalence on home visitor characteristics (demographics, EBP readiness), and client characteristics; those that differ between groups will be included as covariates. We will conduct latent growth curve (LGC) modeling in Mplus to examine the impact of study condition on change over time in primary and secondary outcomes. Mplus provides full information maximum likelihood estimation that produces unbiased parameter estimates under the assumption that the data are missing at random (MAR), and outperforms other missing data approaches even when MAR is not met. Analyses will use a 2 (study condition) X 3 (time) repeated measures intent-to-treat design. First, we will use likelihood ratio difference tests of nested models to determine the overall shape of the individual change trajectories: no change or linear change. Next, we will test unconditional models for all outcomes to obtain the average change effect. Third, we will add study condition to test its impact on initial status and change over time. Model

fit will be evaluated via chi-square, RMSEA, CFI, and TLI, and condition effects will be demonstrated by a statistically significant slope parameter, as tested by the pseudo z test, associated with study condition. For normally distributed outcomes, we will use conventional LGC models, with the appropriate estimator selected based on the distributional properties of the DVs. If client outcomes deviate substantially from normality, we will apply a negative binomial estimator, as recommended for count outcomes (i.e., days of SU) with a distribution that is skewed toward zero. Effect size estimates using Cohen's d will be calculated for all condition effects on client outcomes based on published LGC model recommendations.

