The LGC modeling described above is our preferred approach for analysis. However, given our small sample, we present an alternative analytic strategy in case the longitudinal models fail to converge. If this occurs, we will conduct a series of ANOVAs to test the difference between study conditions on client outcomes separately at each follow-up time point (3- and 6-month), including the baseline value of the outcome as a covariate. Effect sizes will be calculated using Cohen's d .

Exploratory post-hoc analyses using the methods described above will be conducted to examine: (1) condition differences in home visitor-client alliance; and (2) differences in SBI-HV impact based on pregnancy status.

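### Home visiting retention has no usable baseline value, so the planned growth model does not suit it; time already spent in HFA should be a pre-specified covariate for retention and alliance

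*Combined protocol and SAP*

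**What the plan says.** - **Entry.** Criterion 4 under Study Participants, Clients, requires a client to be "enrolled in HFA with a participating home visitor within the prior six months". The recruitment section has home visitors introduce the study "at the enrollment visit (for newly enrolling clients) or at the next available visit", the latter for clients already in the programme.
- **Programme.** Routine HFA Services says that visits "occur weekly for the first 6 months, tapering in frequency over time". It also says: "Families are eligible for enrollment in HFA if they are prenatal or within 2 weeks of the baby's birth".
- **Outcome timing.** Client Measures: "Secondary study outcomes (assessed at baseline, 3-mo, and 6-mo follow-up) include home visiting retention, home visitor-client relationship". Retention is to be taken from the HFA management information system (MIS). No definition by status, visit count or duration is given.
- **Main analysis.** Under SBI-HV Impacts on Client Outcomes, latent growth curve models are used "to examine the impact of study condition on change over time in primary and secondary outcomes". Unconditional models are run for every outcome, and condition is then tested on both initial status and change.
- **Fallback.** If the longitudinal models do not converge, arms are compared separately at 3 and 6 months, "including the baseline value of the outcome as a covariate".
- **Covariates.** Site is always included. Other characteristics enter only if they differ between arms on a baseline test. Time in HFA is not named.

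**The concern.** Retention in home visiting is one of the outcomes named in the primary study aim, so its analysis should work as written. A growth model needs a first measurement that varies between clients and means the same thing as the later ones. Criterion 4 appears to rule that out for retention, because being in the programme is a condition of entry.

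The same criterion admits clients at very different points in the programme. A new client rates alliance (WAI-SC) at the start of the relationship; an established one does so after months of weekly visits. The established client has also already passed through a period in which others may have left. If time in HFA is ignored, retention and alliance trajectories partly describe how long clients had been enrolled, and an uneven mix between arms could be read as a condition effect.

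**Working it through.** The plan gives no retention rate, effect size, SD, intracluster correlation or power, so there is no stated figure to reproduce. The check covers the structure of the model, followed by illustrations under stated assumptions.

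**1. Retention as enrolment status.** Criterion 4 makes the baseline value 1 for all 40 clients.
- The baseline variance is 0, so there is no initial-status variance and no condition effect on initial status to estimate.
- Change adds nothing to follow-up status. With follow-up proportions p1 and p0, (p1 − 1) − (p0 − 1) = p1 − p0.
- In the fallback, the columns are intercept, arm and baseline. Baseline equals the intercept, so three columns have rank 2 and the covariate drops out.

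**2. Retention as visits or months in HFA.** Baseline is now 0 to 6 months of earlier time, or up to about 26 weekly visits. Initial status measures when the client joined, not whether she stays. The only information about retention is what accrues after study baseline, and for visits that also depends on tenure, because frequency tapers after month 6.

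**3. Range of tenure.** HFA enrolment closes 2 weeks after birth and study entry closes 3 months after birth. A client who joined HFA after delivery therefore has at most about 3 months' tenure at entry. Only prenatal enrollees can reach 6 months. At the 6-month assessment, time since HFA enrolment runs from 6 to 12 months.

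**4. Chance imbalance in tenure.** Assume tenure uniform on 0–6 months, 20 clients per arm, and a design effect (DE) of 1 to 1.3.
- SD = 6/√12 = 1.73 months.
- SE of the arm difference = 1.73 × √(2/20 × DE) = 0.55 to 0.62 months, a 95% range of about ±1.1 to ±1.2 months.

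**5. Alliance with no condition effect.** Assume alliance rises with tenure t (months) as 1 SD × (1 − exp(−t/3)), with client SD 1, residual SD 0.5 and no clustering. The expected 6-month change is exp(−t/3) − exp(−(t+6)/3): 0.87 SD at t = 0, 0.32 at t = 3 and 0.12 at t = 6. The pooled slope therefore depends on the client mix even when arms are balanced. For the arm contrast (4,000 simulated trials of 20 against 20, change from baseline to 6 months):

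| Mean tenure gap between arms | Unadjusted bias | Unadjusted false-positive rate | Rate adjusted for tenure |
|---|---|---|---|
| None in expectation | 0.00 SD | 4.4% | 5.3% |
| 1 month | 0.11 SD | 7.4% | 4.9% |
| 2 months | 0.26 SD | 19.4% | 5.3% |

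The adjustment used linear and quadratic tenure terms, and adjusted bias was about 0 throughout. With tenure balanced, the SD of the estimated arm difference was 0.228 unadjusted and 0.234 adjusted, so under this curve the gain is protection against imbalance rather than precision.

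**6. Direct comparison of retention at follow-up.** This is estimable but weak. At 20 against 20, two-sided 0.05, DE 1 to 1.3, power is 25% to 20% for 50% against 70%, and 75% to 63% for 40% against 80% (rates assumed).

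**The case against.** **Retention is undefined, so a 100% baseline is an inference.** This stands. A reader might take it as documented that retention is 100% with zero variance at baseline; that holds only for enrolment status. The visit and duration readings do not rescue initial status, however.

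**The baseline label is loose drafting.** It covers five outcomes at once, and the same section places treatment engagement at 6 months only. That is fair, but the Data Analysis section separately sends all secondary outcomes to the growth model, so the problem does not rest on the label.

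**The fallback already works.** Largely true. Once the constant covariate drops out, the fallback is an ordinary follow-up comparison; under a visit or duration measure, its baseline term would itself act as a tenure adjustment. A reader might infer that retention cannot be analysed at all, and the plan does not support that. But the fallback opens only on non-convergence, so the plan does not route retention to it.

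**Tenure does not bias a randomised comparison.** A reader might infer a bias from an example such as this: with assumed retention of 60% in new and 80% in established clients, arms with 70% and 50% new clients show 0.7 × 60 + 0.3 × 80 = 66% against 0.5 × 60 + 0.5 × 80 = 70%. Those rates and mixes are invented. The 4-point gap is 0.8 of a client in 20, against an SE of √(0.66 × 0.34/20 + 0.70 × 0.30/20) = 14.7 points. Home visitors are randomised and both arms approach all eligible clients with a script, so tenure is balanced in expectation. The 2-month gap in the simulation is more than three times its chance SE, and the covariate rule would probably catch it if tenure were tested. What remains is that home visitors recruit after learning their condition, there are only 10–20 of them, and tenure is not named for testing.

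**Alliance is low-stakes.** The last paragraph of Data Analysis calls it exploratory, and the fallback's baseline adjustment absorbs part of any tenure difference. Both are true. Alliance is also listed as a secondary outcome, and the exploratory analysis uses the same methods.

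**Conclusion.** The point holds for the planned model. Retention has no meaningful baseline under either reading of the term, so a growth model with initial status and slope is the wrong stated analysis for it. A direct comparison of arms at 3 and 6 months remains available. That conclusion follows from criterion 4 and the analysis text and needs no outside figures.

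The tenure part is weaker. Tenure of 0 to 6 months at entry, with the longest values only among prenatal enrollees, is a plausible source of variation that the plan leaves to a baseline test. Between arms it is a risk of imbalance, with a chance range of about ±1.1 to ±1.2 months if tenure is uniform. The documents do not show a bias. All the alliance figures depend on an assumed curve.

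A reader might also infer that the trial's results were distorted. The opening note of the document says that randomisation was eliminated and the planned longitudinal analyses were not carried out, so this is a defect of the plan only.

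**What to change.** 1. In Client Measures, remove baseline as a time point for retention. Define it from the MIS as still enrolled in HFA at 3 and at 6 months after study baseline, with time from study baseline to HFA discharge as a supporting measure.
2. In SBI-HV Impacts on Client Outcomes, take retention out of the growth models. Compare arms directly at each follow-up, with no baseline term and with the adjustment already planned for clustering by home visitor.
3. Record the HFA enrolment date. Pre-specify months from HFA enrolment to study baseline as a covariate for retention and WAI-SC, whatever the baseline tests show.
4. Optionally, describe both outcomes by new and already-enrolled clients. With about 20 clients per arm the cells would be too small for inference.

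The cost is wording plus one covariate in a sample of 40. Checking eligibility already requires the timing of HFA enrolment, and retention already comes from the MIS.
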